6 STUDY DESIGN

6.1 Design Type and Description

This is a Phase 2, randomised, double blind, placebo-controlled parallel group study in adults with mild to moderate AD.

The study will assess the efficacy, safety and tolerability of the treatment of Alzheimer's disease in approximately 300 subjects with LorelcoTM.

After consenting to participate in the study, screening procedures will occur between Days - 24 and -1. All subjects must have measurable mild or moderate Alzheimer's disease, and accordingly screening procedures will include:

- o A positive amyloid biomarker (PET scan) indicative of AD pathology,
- o Mini-mental-state examination (MMSE) score of 22 or greater,
- Free and cued selective reminding test (FCSRT) cueing index of 0.79 or less OR free recall score ≤17
- o Clinical Dementia Rating (CDR) global score of 0.5 or 1.0.
- o A study partner (partner/spouse/carer) consents to the minimum requirements:
 - Study partner will attend at least one screening visit
 - Study partner will be available via phone or in person to provide information to the study as required

Eligible subjects will be randomized in a 1:1 (active:placebo) ratio and return to the study unit on Day 1.

The dosing schedule for subjects is shown in Table 2. The two week initial placebo period will allow for implementation and retraining to assist with dose compliance, without giving participants the intervention drug. The dose level and regime begins at 250 mg a day (Week 3) to monitor for gastrointestinal safety events.

Table 2. Planned Subject Dosing Schedule

Week	Dose Level	Total Daily Lorelco TM Dose (mg)
Week 1 and 2	1 x placebo taken in the morning, with food.	0 mg
Week 3	1 x 250 mg Lorelco [™] (or matching placebo) taken in the morning, with food.	250 mg (or placebo 0 mg)
Week 4 -104	 1 x 250 mg probucol (or matching placebo) taken in the morning, with food. 1 x 250 mg probucol (or matching placebo) taken in the evening, with food. 	500 mg (or placebo 0 mg)

Subjects will self-administer LorelcoTM or placebo in the clinic under the supervision of site staff on Days 1 (±2 days) on Weeks 1, 2, 3, 4, 5, 15, 26, 39, 52, 65, 78 and 104. All other doses will be self-administered at home, or under the supervision of the designated study partner as appropriate. LorelcoTM and Placebo will be provided in a Webster pack or equivalent to assist with dose compliance.

[figure not shown]

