6.7 Dose Stopping Rules and Individual Dosage Adjustments

Dosing may be stopped or modified if suspected adverse drug reactions, changes in vital signs, ECGs, or clinical laboratory results are observed, and these changes pose a significant health risk. Of particular note for dose discontinuation are the following criteria;

- Corrected QT/QTc interval is in excess of 500 ms, or if it increases > 50 ms compared to baseline (baseline will be calculated as the mean of two time points, screening and baseline day 1).
- Occurrence of QT/QTc interval prolongation in association with symptoms of arrhythmia
- Subsequent prescription of a drug with potential QTc prolongation (Antimalarial; Macrolides; Quinolones; Triazole antifungals; Anti-arrhythmic; Antiemetic; Antidepressant; Antipsychotics)
- Evidence of Liver dysfunction, or primary biliary cirrhosis
- If for any reason the Investigator determines that continued participation in the trial is not in the participant's best interest.

The study may be terminated at any point in time at the discretion of the Sponsor.

Clinically or medically significant suspected adverse drug reactions, and SAEs considered to be related to study procedures will be followed until resolved or considered stable.

If an unscheduled interruption of treatment occurs, the PI should notify the Sponsor (via the Clinical Research Organization [CRO]) at the earliest possible time. A missed dose will not be made up. In the event that a patient requires an unscheduled interruption of treatment under conditions other than those associated with toxicity, the case will be reviewed by the PI and the MM, and discussed with the Sponsor/CRO to determine whether such a patient will be allowed to resume treatment.

At the discretion of the Investigator, a participant may be reinstated in the study 4 weeks after discontinuation of the participant. This will be evaluated on a case by case basis, and will also be reviewed by the DSMB. Participants will have a safety evaluation 4 weeks following study drug discontinuation.

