12.3 Procedures and Time Period for Detecting Adverse Events

The Investigator (or designee) is responsible for detection, recording and reporting of events that meet the criteria and definition of AEs.

As a consistent method of soliciting AEs, the participant shall be asked a non-leading question such as: "How do you feel?".

Detection and recording of study related AEs and SAEs extends from the signing of the consent form until completion of the last study related procedure (including follow-up for safety assessments).

Any AE reported or observed after the start of dosing with any study treatment until completion of the last study related procedure (includes follow-up for safety assessments) will be recorded as a treatment-emergent AE.

Any change in health status that is reported or observed after informed consent but prior to starting study treatment and is deemed by the study Investigator to be "not related" to study procedures, will be documented as medical history.

Any pre-existing conditions or signs and/or symptoms present in a patient prior to any involvement in the study (i.e., before informed consent) should be recorded as medical history. In addition, any change in health status, which is reported after informed consent but started prior to informed consent by the volunteer, will be documented as medical history.

Any worsening of a pre-existing condition that occurs following informed consent will be recorded as an AE.

A post-study AE/SAE is defined as any event that occurs outside of the nominal AE/SAE study detection period. Investigators are not obligated to actively seek AEs/SAEs in former study participants. However, if the Investigator learns of any SAE, including a death, at any time after a participant has completed the study and he/she considers the event reasonably

Protocol Version 4, 06 OCT 2021

Confidential

Page 45 of 70

	Study Protocol
Curtin University	Protocol No.: PIA-2020

related to the study treatment, the Investigator will promptly notify the Sponsor.

Patients must be provided with an "Emergency Wallet Card" indicating the name of the study treatment, the study number, the Investigator's name, and emergency contact number.

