12.8 Data Safety Review Committee

A Data Safety Monitoring Board (DSMB), comprised of external parties, has been established for the PIA-Study. Indicated are experienced clinical researchers in geriatric medicine; cardiology and electrophysiology; lipid, stroke and general medicine; cardiovascular medicine and clinical trials; and in data management. The DSMB will initially meet on a quarterly basis (twice) followed by 6-monthly meetings unless deemed required more often. Additional meetings will be held as required on ad hoc basis. To address the risk of QT/QTc prolongation, ECG safety monitoring will be completed and read on site by the study doctor during screening and study visits at baseline and weeks 3, 4, 5, 15, 26, 39, 52, 65, 78, 91, 104, and 4 weeks following completion of the study. Measurement of OT/OTc interval will be completed using automatic algorithms and manual measurement (to the nearest 5 milliseconds and referencing to normal values)²⁰. In the event of a severe adverse effect, such as prolonged QT interval, blinded high quality ECG data will be made available for review by the DSMB. In addition, ECG data will be reviewed by the DSMB 3 monthly (initially) and will be blinded to time, treatment, and subject identifier. Correction of QT interval will be determined using Fridericia's correction: QTcF=QT/RR1/3. Absolute QTc interval prolongation (> 500 ms) and change from baseline in QTc interval (> 50ms) will also be used in consideration for discontinuation or change in treatment protocol. As heart rate can influence corrected OT interval (potential for both over, or under-correction), it is important to ensure that the participant is at rest before and during the ECG. The study doctor will ensure a short rest period prior to administering the ECG to ensure altered heart rate is not a potential confounding factor in QT interval analysis. Furthermore, to ensure interpretation of QT/QTc interval data is correct, the QT/QTc interval data will be analysed using both analyses of central tendency (e.g., means, medians) and categorical analyses (e.g., absolute QTc interval prolongation, change from baseline in QTc interval). If a participant is prescribed a second or subsequent drug with potential QTc prolongation while taking probucol, additional ECGs will be completed to monitor the risk of QTc prolongation. In the event of a severe adverse event, or if prolonged QT/QTc interval continues following discontinuation of LorelcoTM, participants may be referred to a cardiologist.

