13.4 Safety and Tolerability Analyses

Assessment of safety and tolerability is a seondary objective of the study. The analysis will assess the safety and tolerability of LorelcoTM in patients with mild to moderate AD using the safety population.

Safety and tolerability will be assessed through AE, clinical laboratory, vital signs, ECG, and physical examination data. AEs that occur at or after the first dose of Lorelco[™] or placebo will be classified as treatment-emergent adverse events (TEAEs).

The original terms used in the eCRF by Investigators to identify AEs will be coded by system organ class and preferred term using the current version of the Medical Dictionary for Regulatory Activities (MedDRA).

TEAEs will be grouped by system organ class and MedDRA preferred term and summarized by presenting the number and percentage of subjects who experience each TEAE and the number of TEAEs. Summaries by severity (graded according to the NCI-CTCAE v5.0 [or higher]) and relationship to Investigational Product will be provided for all TEAEs. Data listings will also be provided for any deaths, SAEs, and AEs leading to discontinuation of the study.

The actual values and changes from baseline at each post-baseline time point for clinical laboratory parameters, vital signs and ECG parameters will be summarized by visit and timepoint (where applicable). Where applicable, laboratory test results will be graded and summarized according to the NCI-CTCAE v5.0 (or higher). Baseline will be defined as the last assessment prior to the first dose of LorelcoTM/ placebo.

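### Read literally, treatment-emergent AEs and the safety baseline are anchored to the first run-in placebo dose, and the QTc baseline is separately defined in two ways

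*Protocol*

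**What the plan says.** **Run-in.** Section 6.1 and Table 2 give all participants one placebo capsule daily in Weeks 1 and 2, with Lorelco or matching placebo from Week 3. The stated purpose is: "The two week initial placebo period will allow for implementation and retraining to assist with dose compliance, without giving participants the intervention drug". Randomisation comes first: "Eligible subjects will be randomized in a 1:1 (active:placebo) ratio and return to the study unit on Day 1".

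**Treatment-emergent AEs.** Section 13.4 classifies as treatment-emergent "AEs that occur at or after the first dose of Lorelco" or placebo. Section 12.3 uses the same starting point in other words: "Any AE reported or observed after the start of dosing with any study treatment until completion of the last study related procedure".

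**Safety baseline.** In the paragraph on laboratory, vital-sign and ECG changes, Section 13.4 states: "Baseline will be defined as the last assessment prior to the first dose of" Lorelco/placebo.

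**QTc baseline.** For the increase of more than 50 ms, Section 6.7 says "baseline will be calculated as the mean of two time points, screening and baseline day 1". Section 12.8 adds that "change from baseline in QTc interval (> 50ms) will also be used in consideration for discontinuation" or a change in treatment protocol, and also plans a categorical analysis of change from baseline in QTc, without defining baseline.

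**Schedule.** Before probucol starts, Appendix 1 marks ECG and laboratory tests at Screening and at Week 3 Day 1. Visit 0, where randomisation and first dispensing fall, has neither.

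**The concern.** The run-in capsule is placebo and is study treatment, so the plain wording of Sections 12.3 and 13.4 starts the clock at Week 1. Two things follow. AEs arising in Weeks 1 and 2 in the probucol arm are reported as emergent on a drug those patients have not yet taken. In addition, if Appendix 1 is the operative schedule, the last pre-drug ECG and blood tests are handled as on-treatment values rather than as the reference.

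A second problem does not depend on the run-in. An average of two time points and a single last value are different baselines, and the same 50 ms threshold is applied to change from baseline in two sections. Section 4.4 makes QT prolongation the leading safety risk, so the count of patients exceeding 50 ms should have only one possible answer.

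**Working it through.** **1. Which period is the treatment period?** Dosing weeks minus run-in weeks: 104 − 2 = 102. This reproduces the 102-week treatment period in the Section 5 objectives. The synopsis duration entry, read as 2 + 104 = 106, does not. The objectives therefore count from Week 3, while the treatment-emergent window counts from Week 1.

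**2. Unexposed share of the probucol arm's AE window.** 2/104 = 1.92%. With the 4-week follow-up included, 2/108 = 1.85%.

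**3. Dilution of a rate ratio.** Assume a constant hazard and a true ratio RR on drug. The observed ratio is (RR × 102 + 2)/104.

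| Assumed RR | Calculation | Observed ratio |
|---|---|---|
| 1.5 | (153 + 2)/104 | 1.49 |
| 2.0 | (204 + 2)/104 | 1.98 |
| 3.0 | (306 + 2)/104 | 2.96 |

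**4. Patients affected.** At 1:1, 314/2 = 157 per arm. For an event with assumed background 104-week incidence P, the expected number of probucol-arm patients whose first event falls in the run-in is 157 × [1 − (1 − P)^(2/104)]. This gives 0.2 for P = 5%, 1.1 for P = 30% and 4.8 for P = 80%.

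**5. The baseline passages side by side.**

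| Place | What it implies |
|---|---|
| Section 13.4 | One value, the last before the first Lorelco/placebo dose |
| Section 6.7 | Average of screening and baseline Day 1 |
| Section 7.2, criterion 5 | QTcF at screening and pre-dose on Day 1, averaged for eligibility |
| Section 11.5.3 | Triplicate ECGs at screening and before the first dose |
| Sections 11.8 and 12.8 | A baseline ECG listed separately from week 3 |
| Appendix 1 | ECG at Screening and Week 3 Day 1, none at Visit 0 |

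If Section 13.4 is applied with Appendix 1, the only ECG before the Week 1 dose is the screening one. With the 56-day window in the synopsis and Appendix 1, that ECG can be 56 + 14 = 70 days before the first probucol dose. Section 6.1 also gives a 24-day window, which would make it 24 + 14 = 38 days. If instead a Day 1 ECG is done at Week 1, as the other sections may intend, Section 13.4 uses that one. Either way, the Week 3 Day 1 value falls after baseline.

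**6. Effect on the 50 ms criterion.** Assumed readings: screening 420 ms, Day 1 440 ms, on treatment 485 ms.
- Section 6.7: baseline (420 + 440)/2 = 430; change 485 − 430 = 55 ms, above the criterion.
- Section 13.4, last value: 485 − 440 = 45 ms, below it.
- Section 13.4, if only screening precedes the first dose: 485 − 420 = 65 ms, above it.

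**The case against.** The best defence is that a consistent reading exists. Section 6.1 calls the Week 1–2 capsule simply placebo and keeps the pairing of Lorelco with matching placebo for Week 3 onward. Appendix 1 labels the earlier column as pre-baseline. On that reading, the first dose of Lorelco or placebo means the first randomised dose, which fits the Week 3 Day 1 assessments. This may well be the intention. But Section 13.4 does not say so, and Section 12.3, which refers to any study treatment, points the other way.

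It is also fair that Section 6.7 is an individual criterion while Section 13.4 governs group summaries, so different baselines could be deliberate. Section 12.8 weakens this. It uses change from baseline for both discontinuation and categorical analysis, and does not say which baseline applies.

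A reader might infer more than the documents support:
- *The safety comparison is biased.* It is not. The run-in is identical in both randomised arms, and Section 12.4 has onset dates recorded, so these AEs remain separable.
- *Early tolerability is badly diluted.* Section 13.4 plans no early-window comparison between arms. The Section 6.1 early evaluation is a committee review of individual AEs, not a rate ratio.
- *The ECG baseline is the screening value alone.* That holds only under Appendix 1. Sections 7.2, 11.5.3, 11.8 and 12.8 point to a Day 1 or baseline ECG.
- *The run-in causes the QTc conflict.* It does not. An average and a last value differ with or without a run-in.
- *ADAS-Cog has no baseline.* Section 11.6.2 names one, Appendix 1 places it at Week 3 Day 1, and the Section 13.4 sentence belongs to safety.
- *Randomisation should move to after the run-in.* Randomising first is a defensible design choice, and patients lost in the run-in are an ordinary intention-to-treat matter affecting both arms alike.

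**Conclusion.** The point holds as a defect of definition. Taken literally, Sections 12.3 and 13.4 anchor treatment-emergent AEs and the safety baseline to a placebo dose given two weeks before any probucol. For AEs the consequence is minor: 1.9% of the 104-week window, with an assumed ratio of 2.0 appearing as 1.98 under a constant hazard, and between 0.2 and 4.8 of 157 probucol-arm patients affected across the assumed incidences.

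The baseline matters more. The wording decides whether the Week 3 Day 1 ECG and laboratory values serve as reference or as outcome, and the sections do not agree on where Day 1 lies. The QTc conflict between Sections 6.7 and 13.4 stands on its own. The 420/440/485 ms figures are illustrative and say nothing about how often patients would be reclassified. They show only that the same readings can meet the 50 ms criterion under one definition and not the other. The correction is worth making because it is specific and nearly free.

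**What to change.** 1. In Section 13.4, define the analysis baseline for safety summaries as the last assessment before the first dose of randomised treatment (Week 3 Day 1).
2. In Sections 13.4 and 12.3, define treatment-emergent as onset on or after that dose, and list run-in AEs separately by arm. Change only the treatment-emergent flag, not AE recording. Section 12.3 sends unrelated health changes before study treatment to medical history, and that rule must not absorb the run-in.
3. In Section 13.2, say how patients who took only run-in capsules are handled. They stay in the safety population as now worded but would have no treatment-emergent window.
4. State which visit is Day 1, and align Sections 7.2, 11.5.3, 11.8, 12.8 and Appendix 1 with it.
5. Reconcile the QTc baseline across Sections 6.7, 12.8, 13.4 and Appendix 1. If two definitions are intended, name each and say which one every count above 50 ms uses. Which baseline should govern discontinuation is for the sponsor and its safety advisers; this review does not choose.

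The cost is a few sentences in each place. The one visible downside is that run-in AEs move from the main tables to a separate listing. Because item 5 touches an individual stopping criterion, it may not qualify as an administrative amendment under Section 18.3.

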13.5 Pharmacodynamic Analyses

Protocol Version 4, 06 OCT 2021

Confidential

Page 50 of 70

Evaluation of pharmacodynamic parameters is an exploratory objective of this study. Pharmacodynamic marker parameters – observed data and change from baseline – will be summarized using descriptive statistics and graphs (mean \pm SEM) per dose cohort, dose level and time interval as appropriate.

13.6 Efficacy Analyses

The primary analysis was an intention-to-treat analysis of all randomized participants. Data will be analysed using both Generalised Estimating Equations (GEE) and Bayesian Analysis. The analysis of primary endpoints will use linear mixed-effects models, with random slopes and intercepts.

The Alzheimer's Disease Assessment Scale's cognitive subscale (ADAS-Cog) is the standard primary cognitive outcome measure for evaluating treatments in clinical trials of mild-to-moderate AD. But the utility of ADAS-Cog is compromised primarily due to some of its items suffering from either floor or ceiling effects in different stages of AD. The current scoring methodology is also sensitive to missing item responses, scoring errors and variability in the administration of the ADAS-Cog, which are common in clinical trials.

The scoring methodology ADAS-Cog as proposed by Verma et al. will be utilised as it significantly improves the sensitivity of the ADAS-Cog in measuring progression of cognitive impairment in clinical trials focused in the mild-to-moderate AD stage²¹. This scoring methodology also provides a boost to the efficiency of clinical trials requiring fewer patients and shorter durations for investigating disease-modifying treatments. For patients with missing responses to certain items, this new scoring methodology does not require data imputation and estimates cognitive impairment using the set of items answered by the patients.

Analysis of all primary and secondary endpoints contrasting Probucol and placebo, after adjusting for covariates, will use mixed effects-regression with 'random' intercepts and slopes (as has been used for power calculations). Mean differences and associated 95% confidence intervals will be presented for the 'fixed' effect of Probucol treatment.

Further analysis investigating the relationship between change scores (post-minus pre-intervention scores) for the primary ADAS-Cog with MRI volumes (total GM, hippocampus, and medial temporal lobe volumes) and specific blood biomarkers (eg: plasma lipoprotein-Aβ) will be considered using Pearson (or Spearman where appropriate) correlation analysis. For all other correlations between recorded variables that lack an a priori hypothesis, control of statistical errors will be carried out using Holm-Sidak corrections for multiple comparisons.

If Probucol treatment is successful, a directed acyclic graph Bayesian network analysis will be carried out a posteriori on variables identified to be significant predictors of either GM arrest or neuropsychological performance to better elucidate mechanisms of the effect of Probucol. Greedy equivalence search will be used to identify statistical conditional dependencies between variables and directionality will be estimated using the linear, non-Gaussian, acyclic causal models (LiNGAM) approach^{22,23}. Goodness of fit will be estimated using a $\chi 2$ test contrasting the identified model against a saturated model.

In addition to Bayesian analyses, the traditional General Linear Model analysis will also be utilised to compare Probucol to placebo, after adjusting for covariates. The Generalized

Protocol Version 4, 06 OCT 2021

Confidential

Page 51 of 70

Estimating Equations method, which extends the generalized linear model to allow for analysis of repeated measurements or other correlated observations, will also be utilised.

Mean difference and associated 95% confidence intervals will be presented. Data will be analysed using Stata Version 16.

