We have also discovered that probucol (an historic cholesterol lowering drug used to reduce risk for heart disease) profoundly suppresses lipoprotein-amyloid secretion³; promotes lipoprotein-amyloid clearance⁴ and moreover, probucol prevents capillary dysfunction (increased permeability and parenchymal extravasation of plasma proteins⁵. In addition, probucol is a potent modulator of hemoxygenase⁶ and a potent antioxidant⁷, which may explain its profound attenuation of neurovascular inflammation. The synergistic properties of probucol in reducing vascular exposure to potentially toxic blood lipoprotein-amyloid concomitant with potent suppression of inflammation along with evidence that it supports cognitive function in HSHA mice, provides an exceedingly strong rationalization to test this drug clinically. Indirect support for the proposition of pleiotropic effects of probucol is suggested by the ongoing Probucol Trial for Secondary Prevention of Atherosclerotic Events in Patients with Prior Coronary Heart Disease (PROSPECTIVE) trial, a prospective study designed to test the hypothesis that the addition of Probucol to other lipid-lowering drugs will prevent cerebro- and cardiovascular events in patients with prior coronary events and high LDL cholesterol levels⁸.

There have now been approximately 400 clinical trials completed in AD with none targeting peripheral (blood) lipoprotein-amyloid metabolism, or cerebral capillary integrity. There are no studies to date which have demonstrated significant efficacy, or sparing of cognitive

Protocol Version 4, 06 OCT 2021

Confidential

Page 18 of 70

performance in AD. Fortuitously, widespread historic clinical use of probucol demonstrates good tolerability with minimal side effects, or adverse events reported. Hence, rapid translational opportunities may be realized, if efficacy is established.

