13 STATISTICS AND DATA ANALYSIS

Detailed methodology for summaries and statistical analyses of the data collected will be documented in a separate Statistical Analysis Plan (SAP) that will be finalized before database lock. Any changes to the methods described in the final SAP will be described and justified as needed in the Clinical Study Report (CSR).

This section describes the general framework to be used for the analysis and presentation of data in this study. The information described in this section may be revised during the study to accommodate protocol amendments and to make changes to adapt to unexpected issues in study execution and data that could affect planned analyses. All available data will be included in data listings. Data tabulations will be performed for specific analysis populations. No imputation of values for missing data will be performed.

Statistical analyses will be primarily descriptive; no formal hypothesis testing will be conducted. Descriptive statistics will be provided for selected baseline, safety, and efficacy data by dose level and time point as appropriate.

In general, clinical data will be summarized for the dose escalation cohorts and for the dose expansion cohort, separately by each dose level where applicable, using descriptive statistics. Descriptive statistics for continuous data will include means, medians, standard deviations, and ranges, while categorical data will be summarized using frequency counts and percentages. Graphical presentation of selected data may also be performed. Non-zero percentages will be rounded to one decimal place, except 100% will be displayed without any decimal places. For selected assessments, confidence intervals (CIs) will be displayed.

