13.1 Sample Size Considerations

Estimated sample sizes are calculated for the two primary outcome measurements: ADAS-Cog and GM atrophy (hippocampal). In order to ensure that the study has sufficient power to detect differences in both of the primary outcomes, the sample size chosen is the maximum of that calculated for each primary outcome.

The primary analysis was an intention-to-treat analysis and included all randomized participants. Data will be analysed using both Generalised Estimating Equations (GEE) and Bayesian Analysis.

The analysis of primary endpoints will use linear mixed-effects models, with random slopes and intercepts. For the ADAS-Cog, using mixed model analysis published estimates from the ADNI cohort¹⁷ suggest a sample size of 125 AD participants per trial arm (total N = 250) will be required for power at 0.8 to detect a drug effect of 25% over two years and assuming a decline from baseline of 1.10 standardised units on the composite (SD change = 0.83).

Protocol Version 4, 06 OCT 2021

Confidential

Page 49 of 70

Curtin University Study Protocol
Protocol No.: PIA-2020

For the MRI markers, Ledig *et al.* reported the sample sizes required for a 25% intervention reduction over two years based on 322 patients with AD (with 117 followed for 24 months) and a reduction of 10.2% (6.2) for hippocampus¹⁸. Sample size calculations based on hippocampal volume suggest that 93 subjects per treatment arm are required (total N = 186).

Assuming a 20% attrition rate, a sample of 314 subjects will be recruited for the Cognitive study, and 233 subjects will be randomly chosen for the Imaging study.

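### Section 13.6 names plain correlations of ADAS-Cog change with MRI volumes and blood biomarkers and does not mention randomised arm; if both arms are combined, a drug effect on both variables can by itself produce a correlation

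*Protocol*

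**What the plan says.** Section 13.6 (Efficacy Analyses) introduces the analysis as "Further analysis investigating the relationship between change scores (post-minus pre-intervention scores) for the primary ADAS-Cog with MRI volumes" and adds specific blood biomarkers, with plasma lipoprotein-Aβ as the example. The relation "will be considered using Pearson (or Spearman where appropriate) correlation analysis". The synopsis has the same text under Efficacy. Neither place mentions arm, partial correlation or within-arm calculation, and neither says that the arms will be combined.

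For the treatment comparison, the same section does write adjustment down: the analysis "contrasting Probucol and placebo, after adjusting for covariates, will use mixed effects-regression with 'random' intercepts and slopes". The General Linear Model comparison is also described as covariate-adjusted.

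If treatment succeeds, a Bayesian network analysis follows on "variables identified to be significant predictors of either GM arrest or neuropsychological performance to better elucidate mechanisms of the effect of Probucol". Section 13 leaves detailed methodology to a separate SAP, which is not among the documents at hand.

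**The concern.** A Pearson or Spearman coefficient relates two variables and has no place for arm. In a 1:1 trial, a drug that shifts both variables separates the arms on both axes. The combined scatter then shows a trend even if, within each arm, the marker says nothing about cognition.

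The setting makes this worth stating. The one blood marker named is the one the protocol expects the drug to move: Section 4.1 says that probucol "profoundly suppresses lipoprotein-amyloid secretion". The network analysis runs only if treatment succeeds, which is when the arms differ on cognition and the artefact can arise. The Holm-Sidak correction is reserved for other correlations without a prior hypothesis, so it does not cover these.

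At stake is interpretation. A combined coefficient could be reported as a marker tracking cognition when it only restates that both variables differ by arm.

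**Working it through.** **Inputs**
- ADAS-Cog (Section 13.1): the sample size "will be required for power at 0.8 to detect a drug effect of 25% over two years", with a decline of 1.10 and an SD of change of 0.83. Difference = 0.25 × 1.10 = 0.275; d1 = 0.275/0.83 = 0.331.
- Hippocampus (Section 13.1): loss of 10.2%, with the bracketed 6.2 read as the SD. Difference = 0.25 × 10.2 = 2.55; d2 = 2.55/6.2 = 0.411.
- Evaluable numbers (Section 13.1): 186 for hippocampus, 250 for ADAS-Cog.
- Allocation 1:1 (Section 6.1).
- Test level: not stated. Two-sided 0.05 is assumed, in line with the 95% intervals.
- Biomarker effect: not given. 1 to 2 SD is assumed.

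**Reproducing the plan's figure.** n per arm = 2 × (1.960 + 0.842)² × 6.2²/2.55² = 92.8, so 93, as stated. This supports reading 6.2 as the SD. Attrition: 186/0.8 = 232.5, so 233, as stated.

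**Induced correlation.** Let each variable have SD 1 within arm, with zero within-arm correlation. Combining two equal arms gives covariance d1·d2/4 and variances 1 + d²/4, so in absolute value

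r = (d1·d2/4) / √[(1 + d1²/4)(1 + d2²/4)].

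With the Fisher transformation, m = atanh(r)·√(n − 3), and the chance of p < 0.05 is Φ(m − 1.96) + Φ(−m − 1.96).

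*Planned effects:* r = 0.0341/√(1.0274 × 1.0423) = 0.033. At n = 186, m = 0.033 × √183 = 0.445, and the chance is 0.065 + 0.008 = 7.3%. The |r| needed for p < 0.05 at this n is 0.144.

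*Biomarker, with d1 = 0.331:*

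| Assumed biomarker shift | r | Chance of p < 0.05, n = 250 | n = 186 |
|---|---|---|---|
| 1 SD | 0.07 | 21% | 17% |
| 2 SD | 0.12 | 45% | 35% |

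**Simulation check, 20,000 trials per scenario.** Combined arms gave 7.5% for the planned effects at n = 186, and 21.4% and 44.7% for biomarker shifts of 1 and 2 SD at n = 250. Centring both variables within arm, which is the arm-adjusted partial correlation, gave a mean r of about 0.00 and 5.0% to 5.3% in every scenario run.

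**The case against.** The strongest reply is that the flaw is read from silence. A reader might infer that the plan pools the arms and leaves arm out. The text does not say so: both coefficients can be computed within arm, the wording is tentative, and the SAP may settle the matter. That stands, so the point is conditional. It does not disappear, because the protocol names a specific two-variable method here and writes adjustment down for other analyses in the same section.

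Other replies that stand:
- **Size.** On the protocol's own figures the excess is about two percentage points on a secondary correlation.
- **Biomarker figures.** A reader might take 21% to 45% as the expected error rate. It is not: Section 4.1 describes the suppression in words only. Plasma lipoprotein-Aβ is also absent from the laboratory evaluations (11.8), the blood-volume table (11.10), the schedule (Appendix 1) and the laboratory list (Appendix 2), so n = 250 for it is an assumption too.
- **Variables.** The change-score wording attaches to ADAS-Cog. If the MRI and biomarker values are baseline levels, randomisation balances them in expectation and the artefact does not arise.
- **Meaning.** A reader might conclude that a combined correlation is spurious. It may partly reflect a real path from drug to marker to cognition; the difficulty is that it cannot tell this from parallel effects.
- **Role.** A reader might treat these correlations as the protocol's evidence on mechanism. Section 13.6 gives that task to the network analysis and does not say that the correlations choose its inputs.

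**Conclusion.** The point holds as a minor improvement to a stated method. If the correlations are computed across arms on change or post-treatment values, they can show an association that does not exist within arms. For hippocampal change at the planned effects this is almost negligible (r = 0.03, 7.3% against 5% at n = 186). It matters only for a marker the drug moves strongly, and there its size rests on an assumed 1 to 2 SD shift, an assumed n and a two-sided 5% level. The documents do not support a claim that the arms will be pooled, that any correlation found would be false, or that the mechanism conclusions depend on these coefficients. The primary comparison of probucol with placebo comes from the mixed model and is unaffected.

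**What to change.** In Section 13.6 and the synopsis, state that these are partial correlations (Pearson or rank) adjusted for randomised arm, with the coefficient in each arm also shown. State that the MRI and biomarker values are change scores, if that is intended. The within-arm coefficients show whether one common association is a fair summary. Adjustment for baseline values is not needed to remove this artefact. The cost is one phrase in two places and one degree of freedom, with no extra data or participants. If the SAP already specifies this, the change only aligns the protocol with it.
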